Appendix 1 – ECOG Performance Status

Appendix 2 – Ramucirumab- Additional Information

1. STUDY RATIONALE

Biliary cancers are a heterogeneous group of malignancies with a limited number of chemotherapeutic options in advanced disease. The current standard of care for palliative treatment of biliary cancers is the combination of gemcitabine and cisplatin¹. There is no clear second-line therapy in biliary cancers after progression on gemcitabine and cisplatin. A retrospective study of second-line therapies at MD Anderson demonstrated a median progression free survival in this population of 2.7 months with a multitude of therapies used². Angiogenesis has been shown to be a potential target for biliary cancers in a variety of small phase II studies³⁻⁵. Ramucirumab is a novel monoclonal antibody that targets the vascular endothelial growth factor receptor 2 (VEGFR2). It is FDA-approved for the treatment of advanced gastric cancer, and inhibits tumor-induced angiogenesis through high affinity binding to VEGFR2⁶.

2. BACKGROUND

2.1 Biliary Cancers

Biliary cancers are comprised of intrahepatic cholangiocarcinoma, extrahepatic cholangiocarcinoma, and gallbladder carcinoma. They are an aggressive group of malignancies but heterogeneous in their presentations and clinical pictures. The majority of patients present at an advanced stage, and median survival of locally-advanced or metastatic biliary tract cancers is less than one year. These malignancies are characterized by lymph node involvement and distant metastases⁷.

Gallbladder cancer (GBC) is the most common form of biliary tract cancers. Internationally, Israel has the highest incidence worldwide, with 7.5 cases per 100,000 men and 13.8 cases per 100,000 women. Other countries with significant incidence rates include Mexico, Bolivia, Chile, and northern Japan⁸. In the US, about five thousand new cases are reported every year. The incidence has been on the decline owing to the increase in the number of cholecystectomies for other reasons like acute or chronic symptomatic cholecystitis. Less than 10 percent of patients with GBC live more than five years after diagnosis. The mortality is very high and is attributed to the late diagnosis and an advanced stage of the disease⁹.

At the same time, cholangiocarcinoma is a highly fatal cancer of the biliary tree. In the United States, approximately 5,000 new cases of cholangiocarcinoma are diagnosed annually; these cases are equally distributed between intra-hepatic cholangiocarcinoma (ICC) and extrahepatic cholangiocarcinoma (ECC)¹⁰. Data from the National Cancer Institute's Surveillance, Epidemiology and End Results (SEER) indicate that the incidence of ICC is increasing¹¹. The incidence of ICC in the US almost tripled between 1975 and 1999¹². The reasons behind this increase are not clear.

Chemotherapy for biliary cancers

Gemcitabine has been the mainstay of chemotherapy in biliary cancers. The ABC-01 study was a phase II trial that examined the combination of gemcitabine and cisplatin in advanced biliary cancers. 86 patients were randomized to gemcitabine alone versus the doublet regimen. The primary endpoint of 6-month progression-free survival was 45.5% vs. 57.1% in the two arms with median time to progression being 8 months with the gemcitabine and cisplatin combination¹³. The benefit of the addition of cisplatin to gemcitabine was verified with the ABC-02 study, a randomized phase III trial of 410 patients with overall survival as the primary endpoint. The authors found that the combination of gemcitabine and cisplatin significantly improved median overall survival (11.7 months vs. 8.1 months) and progression-free survival (8.0 months vs. 5.0 months) compared to gemcitabine alone¹.

Therapy in refractory biliary cancers

There has not been any randomized controlled phase II or III trials of second or third-line therapies in biliary cancers thus far. A recent review of second-line therapy that included 14 phase II trials indicated a mean overall survival (OS) of 7.2 months, progression-free survival (PFS) of 3.2 months and response rate (RR) of 7.7% with second-line therapy¹⁴. Similarly, a large retrospective review of second line therapy for 300 BC patients from Italy also showed a median OS of 7.2 months¹⁵. A retrospective review from MD Anderson Cancer Center indicated a median PFS of 2.7 months (95% CI 2.3-3.8 months) with a median OS of 13.8 months (95% CI 12-19.3 months) in those receiving second-line chemotherapy for cholangiocarcinoma². There is no “standard” second-line chemotherapy after gemcitabine and cisplatin; FOLFOX, irinotecan, capecitabine and erlotinib are used in practice¹⁶⁻²⁰.

Rationale for targeting angiogenesis in biliary cancers

Expression of pro-angiogenic factors such as VEGFs and angiogenesis play an important role in biliary cancers. VEGF and VEGFR overexpression has been reported in 30-50% of biliary cancer cases and are associated with worse prognosis²¹⁻²³. Estrogens interact with insulin-like growth factor (IGF1) and its receptor (IGF1-R) to simulate the growth of cholangiocarcinoma. Estrogens also stimulate the expression and secretion of VEGF-A, VEGF-C and VEGFRs in cholangiocarcinoma cell lines potentially altering cholangiocarcinoma proliferation and tumor neoangiogenesis²⁴. Conversely, inhibition of cholangiocarcinoma proliferation also inhibits VEGF expression. Endothelin 1 (ET-1) inhibited the proliferation of cholangiocarcinoma xenografts in nude mice, which was associated with a down-regulation of VEGF-A and VEGF-C expression²⁵.

A phase II trial of gemcitabine, oxaliplatin, and bevacizumab enrolled 35 patients with biliary cancers and resulted in a RR of 40% and PFS/OS of 7.0/12.7 months, which compared favorably with historic controls⁵. Lubner and colleagues reported a multicenter phase II trial of bevacizumab and erlotinib in patients with unresectable biliary cancer. The confirmed partial response rate in this study was 12%, median OS was 9.9 months, and TTP was 4.4 months, suggesting an effect of bevacizumab in this disease⁴. In the ABC-03 trial, Valle and colleagues examined the effects of adding cediranib, a pan-VEGF receptor tyrosine kinase inhibitor, to traditional treatment with cisplatin/gemcitabine. This group performed a randomized phase II

study that included 124 chemotherapy-naive biliary cancer patients who received cisplatin/gemcitabine with or without cediranib. Patients assigned to cediranib had a significantly improved RR compared with patients assigned to placebo. (44% vs. 19%, respectively ($p = .0036$). Patients receiving placebo were also more likely to progress (28% progressive disease vs 10% for cediranib). However, this did not result in improved OS²⁶. Modest anti-tumor efficacy against biliary cancers was also demonstrated with multi-targeted anti-angiogenic tyrosine kinase inhibitors including sorafenib and sunitinib^{3,27-29}.

Ramucirumab is a fully human IgG1 monoclonal antibody that is a specific and direct inhibitor of VEGFR-2, where it binds to the extracellular VEGF-binding domain with high degree of specificity and affinity, at picomolar dose range. It thus prevents the binding of the VEGF ligand to the VEGF-R2 receptor. In the phase I trial for patients with advanced solid tumors, ($n=37$) ramucirumab demonstrated encouraging early evidence of efficacy at a range of dose levels including the one enrolled patient with biliary cancer who experienced stable disease lasting over 5 months³⁰. Ramucirumab was recently shown to improve survival compared with placebo in advanced gastric cancer, with a median overall survival of 5.2 months in the ramucirumab arm, and 3.8 months in the placebo arm. The main toxicity seen was an increase in hypertension in the ramucirumab group³¹. Additionally, a double-blind, randomized, phase III study of previously treated gastric and gastroesophageal junction cancers included 665 patients randomized to ramucirumab plus paclitaxel versus placebo plus paclitaxel³². In this study, the combination arm showed an improvement in overall survival (9.6 months vs. 7.4 mths, $p=0.017$), providing further rationale for the use of ramucirumab in refractory gastric cancer.

Initial data with ramucirumab in biliary cancer

In the initial 43 patient cohort that was enrolled in this phase II trial, 42 patients with cholangiocarcinoma and gallbladder cancers received treatment. Ramucirumab was well tolerated with 9 grade 3 toxicities including anorexia, dehydration, hypertension, hyponatremia, proteinuria and vomiting. There were no grade 4 toxicities. The median PFS for all patients who received treatment was 2.73 months (95% CI 1.91-8.03 months) and median OS was 6.31 months (95% CI 4.7 months – not reached). The overall response rate was 0% and disease control rate (SD + PR + CR) was 44%. Importantly, 6 patients (13%) were on treatment for > 24 weeks. Of these, 3 were on treatment for at least 44 weeks. In reviewing the genomic data on the 6 patients with prolonged periods of stable disease, we noted that 4 of the 6 harbored mutations in DNA repair pathways (BRCA, FANCA, ARID1A) and 1 patient had an FGFR alteration

3. DRUG INFORMATION

3.1 RAMUCIRUMAB

1. The Product

Ramucirumab is an anti-VEGF Receptor 2 recombinant human monoclonal antibody of the IgG1 subclass. Ramucirumab drug product is a sterile, preservative-free solution for infusion of ramucirumab formulated in an aqueous solution at a concentration of 10 mg/mL (500 mg/50-mL vial). The buffer contains 10 mM histidine, 75 mM sodium chloride, 133 mM glycine, and 0.01% polysorbate 80. It is administered as an intravenous infusion at a dose of 8 mg/kg over 60 minutes every two weeks.

2. Indication

In the United States, ramucirumab is indicated for the treatment of advanced gastric and gastroesophageal cancers either alone or in combination with paclitaxel after prior fluoropyrimidine- or platinum-containing chemotherapy.

It is also indicated in combination with docetaxel for treatment of metastatic non-small cell lung cancer with disease progression after platinum-therapy.

Accessed via: <http://pi.lilly.com/us/cyramza-pi.pdf>

3. Introduction

Ramucirumab is a recombinant human monoclonal antibody of the immunoglobulin G subclass 1 that specifically binds to the extracellular domain of the VEGFR2. This prevents the binding of activating ligands (VEGF-A, VEGF-C, VEGF-D) to the receptor. This inhibition results in inactivation of downstream signaling pathways that promote migration and proliferation of human endothelial cells.

4. Preclinical Studies with Ramucirumab

Preclinical pharmacodynamic data demonstrated that ramucirumab binds specifically and with high affinity to human VEGFR2, and not to murine VEGFR2 or the related human VEGF receptors, VEGFR-1 and VEGFR-3. Furthermore, a surrogate antibody for ramucirumab was tested with demonstration of potent antiangiogenic effects in multiple mouse xenograft solid tumor models, including gastric, hepatic, breast, colorectal, non-small cell lung, and pancreatic cancer models (Ramucirumab investigator's brochure).

5. Clinical Studies In Gastrointestinal malignancies with Ramucirumab

The REGARD trial randomized patients with advanced gastric or GE junction cancers in a 2:1 fashion to ramucirumab versus best supportive care. These patients had previously received platinum or fluoropyrimidine therapy. Patients who received ramucirumab has an improvement in 12-week PFS from 15.8% to 40.1% with overall survival being significantly improved as well (5.2 vs. 3.8 months)³¹.

The RAINBOW trial randomized 665 advanced, refractory gastric or GE junction patients to receive paclitaxel plus ramucirumab versus paclitaxel plus placebo. The addition of ramucirumab to paclitaxel significantly improved median PFS from 2.9 months to 4.4 months. Objective response rate was similarly improved from 16% to 28%. Further, the combination of paclitaxel with ramucirumab resulted in a significant improvement in overall survival from 7.4 months to 9.6 months³².

6. Potential Risks of Ramucirumab Toxicities

The most common toxicities reported with Ramucirumab as monotherapy include hypertension (16%), diarrhea (14%), headache (9%), and hyponatremia (6%). Class-related effects such as hemorrhage (3.4%), arterial thromboembolic events (1.7%), and gastrointestinal perforations (0.7%) were rarely noted. Infusion-related reactions were initially seen in 16% of patients prior to the institution of premedication recommendations.

7. Further Information and Storage

See Appendix 2 for Package Insert and Investigator's Brochure

4. OBJECTIVES

PRIMARY

Determine the progression-free survival (PFS) of ramucirumab in advanced biliary cancers (intrahepatic cholangiocarcinoma, extrahepatic cholangiocarcinoma, and gallbladder cancer) who have received prior chemotherapy.

SECONDARY

- Determine the response rate (RR) and disease control rate (partial response + complete response + stable disease) of ramucirumab in advanced biliary cancers
- Determine overall survival (OS) of ramucirumab in advanced biliary cancers
- Evaluate the toxicity of ramucirumab in advanced biliary cancers

EXPLORATORY

- Correlate the carbohydrate antigen (CA) 19-9 response (defined as >50% decrease from baseline) with tumor response, PFS and OS
- Correlate baseline tumor gene expression profile with PFS
- Correlate pre- and post-therapy CT imaging to quantify iodine content, atomic numbers, and Z-values and correlate with response

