10. Hematology: complete blood count with differential. Chemistry: glucose, creatinine, BUN, total bilirubin, AST, ALT, alkaline phosphatase, albumin, LDH, total protein, and electrolytes (sodium, potassium, phosphorus, chloride, C02, magnesium, calcium). Tumor markers (CA19-9) as indicated. Tumor markers are performed every 2 cycles. In patients with known Gilbert's syndrome, it is recommended to perform a direct bilirubin and indirect bilirubin.
11. Within 10 days of decision to discontinue study treatment.
12. At 28-45 days from last dose of study medication.

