10. STATISTICAL METHODS

10.1 Study design and sample size

This is a single arm, open label, phase II trial to assess the efficacy and toxicity of ramucirumab in patients with pre-treated, advanced bile duct cancer. The primary objective is to evaluate the efficacy of the therapy. The primary endpoint is the progression-free survival (PFS). A maximum of 60 patients will be enrolled in the study at an estimated accrual rate of 2-3 patients per month. The study will monitor for futility and safety so that it will stop early if based on the interim data, it is unlikely the PFS will be better than that estimated from historical data or the study drug is too toxic.

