10.6 Analysis method

Data analysis will be performed using SAS or S-plus, as appropriate. The median PFS time will be estimated by Bayesian posterior estimates, along with the 95% credible interval. Toxicity will be reported by type, frequency and severity. Highest toxicity grades per patient per course will be tabulated for adverse events and laboratory measurements.

Demographic and baseline laboratory results will be summarized using descriptive statistics, including means with standard deviations, or medians with ranges, histograms and box-plot. Fisher's exact test and Wilcoxon rank test will be used in the data analyses of categorical and continuous variables, respectively. Progression-free survival and overall survival functions will be estimated using the Kaplan-Meier method. The two-sided log-rank test will be used to assess the differences of time to events between groups, and Cox proportional hazards model will also be fitted to evaluate the association between time-to-event outcomes and tumor gene expressions. The correlation between pre- and post- therapy CT imaging results will be assessed through Spearman correlation and Wilcoxon signed rank test will be used to assess whether the change in CT imaging between pre- and post-therapy is statistically significant. In addition, logistic regression analyses will be performed to assess the association between CT imaging results or CA19-9 response (defined as >50% decrease from baseline) and tumor response.

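### The exploratory CA 19-9 analysis of PFS and OS uses only a yes/no fall of more than 50%; a continuous log-change covariate, tied to a landmark or made time-dependent, would usually use the data better

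*Combined protocol and SAP*

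**What the plan says.** The section 4 exploratory objective is to correlate CA "19-9 response (defined as >50% decrease from baseline) with tumor response, PFS and OS". Section 10.6 uses the same definition, but only for logistic regression linking CT imaging results or "CA19-9 response (defined as >50% decrease from baseline) and tumor response". For time-to-event outcomes it says "The two-sided log-rank test will be used to assess the differences of time to events between groups". It adds a Cox model, which is to "evaluate the association between time-to-event outcomes and tumor gene expressions"; CA 19-9 is not named there.

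The marker is collected repeatedly. Section 7 lists CA 19-9 among the Day 1 assessments of each 14-day cycle. Footnote 10 to Table 7 says instead that markers are taken as indicated, and then "Tumor markers are performed every 2 cycles". Section 10.2 counts PFS from treatment start. On sample size, section 10.1 says "A maximum of 60 patients will be enrolled in the study". No power, significance level, effect size or expected responder share is given for the CA 19-9 analysis, and no reason for choosing 50%.

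**The concern.** A two-group variable treats a 49% fall and a five-fold rise as the same result. If prognosis shifts gradually with the marker, a log-rank test of responders against the rest sets aside information already collected. The loss grows as the responder group shrinks. In a trial of at most 60 patients, a real association could then be reported as absent.

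There is also a timing problem. A fall is observed only after treatment has started, yet PFS runs from treatment start. Patients counted as responders must have stayed event-free long enough to show the fall, and neither a landmark nor a time-dependent analysis is specified. This affects the binary comparison as planned, and would equally affect a continuous analysis of best change.

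**Working it through.** **Inputs from the documents.** At most 60 patients (10.1); 35 PFS events in the precision statement (10.2); two-sided log-rank test (10.6).

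**Assumed inputs.** Two-sided 5% level; log CA 19-9 change normal and linear in the log hazard; responder share p between 10% and 50%; in the main simulation, 90% of patients with an event and a hazard ratio of 1.5 per SD.

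**Step 1: the plan's own figure.** None exists for CA 19-9. As a check on the 35-event input, the section 10.2 interval can be recomputed under an exponential model with the section 10.3 prior. The posterior is IG(2.5625 + 35, 4.6875 + 35 × 3), which gives 2.17 to 4.14 months. This agrees with the stated 2.1 to 4.2 to within 0.1 month.

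**Step 2: information kept by the cut.** For a normal covariate split at responder share p, relative information = φ(z_p)² / [p(1 − p)].
- p = 50%: 0.399² / 0.25 = 0.64
- p = 30%: 0.348² / 0.21 = 0.58
- p = 20%: 0.280² / 0.16 = 0.49
- p = 10%: 0.1755² / 0.09 = 0.34

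**Step 3: effect on power.** If the continuous analysis has 80% power, binary power = Φ[(1.96 + 0.84) × √(relative information) − 1.96]. At p = 20% this is Φ(2.80 × 0.70 − 1.96) = Φ(0.00) = 0.50.

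The simulations compare the Cox score test on the continuous value with the log-rank test on the split, in 60 patients. The 35-event runs use a hazard ratio of 0.62 per SD, chosen for a nominal 80%.

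| Responder share | Information kept | Formula (continuous 0.80) | Simulation, 90% events, HR 1.5 per SD (continuous 0.80) | Simulation, 35 events (continuous about 0.77) |
|---|---|---|---|---|
| 50% | 64% | 0.61 | 0.61 | 0.58 |
| 30% | 58% | 0.57 | 0.52 | 0.44 |
| 20% | 49% | 0.50 | 0.43 | 0.35 |
| 10% | 34% | 0.37 | 0.28 | 0.20 |

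By the formula, more than half of the information is lost only below a share of about 21%. Power drops below 40% only below a share of about 12%.

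**Step 4: the opposite case.** Suppose the hazard changes only at the 50% cut, with a hazard ratio of 0.35, 60 patients and 50 events. Binary power is then 0.44, 0.73 and 0.87 at shares of 10%, 20% and 30%, against 0.24, 0.49 and 0.67 for the continuous test. The ordering reverses.

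**Limit.** All these runs fix the covariate at time zero. They isolate the loss from the cut and say nothing about the size of the timing bias.

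**The case against.** A pre-specified responder definition is a legitimate exploratory objective, and section 10.6 does not forbid a supplementary continuous analysis. The simulations in steps 2 and 3 generate data from the model that the continuous test assumes, so they favour it; step 4 shows that a true threshold favours the cut. Both points stand. They are the reason to keep the >50% fall as a secondary summary. They do not justify making it the only analysis, since the documents cite no evidence for a threshold at 50%.

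A reader might infer that the cut discards most of the power. The documents do not support that. It needs a low responder share and a near-linear effect, and neither is given. At a 50% share in the 90%-event runs, 0.61 of 0.80 is kept, about three quarters.

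A reader might also take the first cohort's result, "The overall response rate was 0% and disease control rate (SD + PR + CR) was 44" percent, as showing that marker responders will be rare. That figure is tumor response, a different measure. It makes a small group plausible but does not establish it, and no CA 19-9 trajectories are reported.

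**Conclusion.** The concern holds in limited form. The plan relates CA 19-9 to PFS and OS only through a yes/no cut. Under a normal, linear log-change model that cut loses about 36% of the information at best (50% share) and about 66% at a 10% share. The corresponding fall in power is from about 0.80 to between 0.61 and 0.28 with 60 patients, 90% events and a hazard ratio of 1.5 per SD. The actual loss depends on a responder share and a shape of effect that the documents do not give, and it becomes a gain if the effect is a true threshold at 50%. Changing the scale alone would not remove the guaranteed event-free time, so the timing must be specified as well. The primary endpoint, stopping rules and sample size are unaffected. Priority is low.

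**What to change.** In sections 4 and 10.6:

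- Make the main CA 19-9 analysis for PFS and OS a Cox model with log2(CA 19-9/baseline) as a continuous covariate. Enter it either as a time-dependent covariate or as the value at a fixed early landmark, with PFS and OS counted from that landmark. Do not use best change over the study.
- Report the hazard ratio per doubling with a 95% CI, and check linearity with a spline or residual plot.
- Keep the pre-specified >50% fall as a secondary summary, analysed from the same landmark.
- State how patients with a normal baseline CA 19-9 are handled.
- Reconcile the two CA 19-9 schedules, Day 1 of each cycle in the section 7 list and every 2 cycles in footnote 10 to Table 7, since the choice of landmark depends on them.

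The cost is wording, with no new patients or visits. Linearity on the log scale is assumed, and power is lower if the effect is a true threshold at 50%. A landmark also drops patients with an event before it. As a rough guide, with exponential PFS and the 3-month median of section 10.2, a 4-week landmark (two cycles, 0.92 months) would exclude 1 − 2^(−0.92/3) = 19% of patients from the PFS analysis. A time-dependent covariate avoids that exclusion but needs the repeat values to be collected on one consistent schedule.
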